10.2 Statistical analysis plan

The primary objective of the statistical analysis is to compare the effects of cigarette ventilation between two study groups: ventilated filter cigarettes and unventilated filter cigarettes. All statistical analyses will be performed using SAS version 9.4 (SAS Institute Inc., Cary NC) and a p-value less than 0.05 will be considered significant.

Describing the Study Population

Descriptive statistics will be performed for data collected on demographic characteristics, subjective measures and biomarkers at different phases and visits. Baseline data will be compared between the two ventilation groups with the two-sample t-test or the non-parametric Wilcoxon rank sum test for continuous or ordinal variables and chi-square tests for categorical variables. Biomarker data may be log transformed if necessary.

Primary Endpoint Analysis

The primary endpoints are (1) the total NNAL at the 6-week visit adjusted for NNAL at end of Phase 2 (visit 00); and (2) the mean CPD based on 7 days ITR data before week 6 visit adjusted for the mean CPD during Phase 2 (visit 00). The analysis of these two endpoints will evaluate non-inferiority of the unventilated group compared to the ventilated group.

Primary Analysis

The primary analysis will be a one-sided, two-sample t-test for non-inferiority. The null hypothesis for total NNAL (analyzed in the log scale) is that the increase from end of Phase 2 (visit 00) is 15% greater in the unventilated group compared to the ventilated group. The NNAL alternative hypothesis is that the increase from baseline (visit 00) is no higher than 15% in unventilated over ventilated groups. If the null hypothesis is rejected in favor of the alternative hypothesis, we will conclude that the unventilated filters are no more harmful in terms of NNAL exposure than the ventilated filter and may actually be less harmful. Similarly for the CPD, the non-inferiority t-test will have a null hypothesis that the 6 week mean increase in CPD from end of Phase 2 (visit 00) for the unventilated group is greater than 2.0 cigarettes compared to the ventilated group. The alternative hypothesis is that the CPD increase in the unventilated group is no more than a mean of 2.0 cigarettes verses the CPD increase in the ventilated group and the unventilated group may even smoke fewer cigarettes.

Secondary Analysis

The above methods will be supplemented with multiple linear regression analysis to include the baseline (visit 00) value for NNAL or CPD and the stratification variable (site), plus any other subject specific characteristics which might not be balanced between the study groups (p-value<0.2).

Finally, NNAL and CPD will be analyzed for all visits, starting at visit 00, using a linear mixed effects model (SAS PROC MIXED). The fixed effects are ventilation group indicator, plus other potential predictors. To model the variation within subjects, several candidate variance-covariance structures will be compared using both graphical and information criteria. Variance parameters will be estimated using restricted maximum likelihood method with the Satterthwaite approximation. This analysis will provide useful information about the change in toxicant exposure and the change in the number of cigarettes smoked per day over time.

Both linear regression models and repeated measures analysis can be modified for the equivalence and non-inferiority testing situations.³⁴

Secondary Endpoint Analysis

The secondary analyses include the other biomarkers (as listed above). The analysis for these potential toxicants will be the same as that outlined above for NNAL with measurements at end of Phase 2 (visit 00) and at the 6 week visit. A non-inferiority margin has not been established for many of these biochemical measures. Instead, group differences or ratios (if in the log scale) will be estimated with their 95% CI and examined as to whether or not they contain 0 for differences or 1 for ratios. Inhalation measures and smoking intensity (solanesol levels in the filter butts) will be analyzed with similar methods as the change in biomarker and CPD with regression models incorporating-covariates for baseline variables that may be different between groups ($p\text{-value}<0.2$). The FTND as a measure of dependency is a composite score that ranges from 0 to 10. With the expectation of non-inferiority for the unventilated group, a linear regression model for FTND at 6 weeks will include the FTND at baseline (visit 00) and the ventilation group indicator, plus any other important subject characteristic. The 95% CI for the estimated coefficient for the group indicator will be calculated to verify that it contains the value zero, indicating no difference in dependency between ventilation groups. The mCES and PHR questionnaires produce a series of subscales. To identify differences between ventilated and unventilated groups, non-parametric methods will be utilized, first with the Wilcoxon signed rank test to check for changes from end of Phase 2 to 6 weeks within each ventilation group and then with the Wilcoxon rank sum test for differences between groups.

Exploratory Analysis

The exploratory analysis for the other volatile organic biomarkers (listed in section 6.2) will be the same as that outlined above for NNAL and the other secondary biomarkers.

Correlation procedures (Pearson and Spearman) will measure the degree of association for the same biomarkers assayed from two or more biosamples.

Safety Endpoints

AEs and SAEs will be recorded as described in the Adverse Event SOP. AEs and SAEs will be tabulated separately for the two groups. We expect study product-related AEs and SAEs to be rare in this trial and, therefore, no formal statistical comparison of the rate of AEs and SAEs across treatment groups is planned for this trial.

Missing Data

Every effort will be made to limit the amount of missing data in this trial. Study participants will be incentivized to attend study sessions. That said, some level of missing data is inevitable in a study of this kind. We will compare subjects who do and do not complete the study sessions in order to identify baseline covariates associated with study completion.

Our primary approach to handling missing data will be a sensitivity analysis using multiple imputation with the Markov Chain Monte Carlo (MCMC) method³⁵ carried out in PROC MI in SAS, where missing values are imputed using regression models developed from baseline covariates. Values can be imputed for both continuous and categorical variables. If the ventilation groups are associated with missing data, we will conduct multiple imputation for each ventilation group separately. Following imputation, standard statistical methods can be applied. A final single

assessment of ventilation group difference will be obtained from combining the results across the imputed datasets using PROC MIANALYZE in SAS.

Interim Analyses

No interim analysis is planned.

11 Supporting Documentation and Operational Considerations

Informed Consent Procedure and Documentation

Potential subjects will be told the nature of the research over the phone during screening and then at a virtual orientation meeting where the study is described in detail. All potential study participants will be provided a copy of the IRB-approved consent form to review prior to signing. They will be told they may discontinue participation at any time and will not be discriminated against if they choose to do so. Subjects will be told their participation in the project will be strictly confidential, that any identifying information will be available to the project investigators or institutional or federal regulatory groups only, and that no identifying information concerning the data and results will be made known. The investigator or designee will explain all aspects of the study in lay language and answer all questions regarding the study. Subjects will be required to demonstrate an understanding of the study purpose and procedures prior to signing the consent form. If the participant decides to participate in the study, he/she will be asked to sign and date the consent document and will receive a copy for their records. Consent form must be signed before the research is started.

Confidentiality of Data

Participation in the project will be strictly confidential, any identifying information will be available to the project investigators and institutional or federal regulatory groups only, and no identifying information concerning the data and results will otherwise be made known. All raw data will be coded with numbers and any form with identifying information (e.g. consent forms) will be kept electronically in a password protected database. Subjects will have written assurance that while de-identified individual subject data may be available to other researchers for research purposes, only a summary of the results will ever be published or otherwise publicly released. Identifying information (initials and telephone numbers) entered in the Daily Text system will not be shared nor extracted with the data by the Biostatistics and Data Management Core.

All data will be de-identified and posted on a secure, password-protected website that is only available to research investigators (both inside and outside the institutions affiliated with the Program Project Grant) due to data sharing requirements; subjects will be informed of this during the informed consent process.

The data from these studies will not be used to direct patient care. Therefore, participation in this study will have no influence on the care the subject receives nor will it influence treatment decisions. If subjects would like their information on vitals or other findings released to another party, they will be asked to sign a release of information form.

To help protect the participant's privacy, a Certificate of Confidentiality from the National Institutes of Health is in place. With this certificate, the researchers cannot be forced to disclose information that may identify the participants, even by a court subpoena, in any federal, state, or local civil, criminal, administrative, legislative, or other proceedings. The researchers will use the Certificate to resist any demands for information that would identify the participants, except as explained below. The Certificate cannot be used to resist a demand for information from personnel of the United States Government that is used for auditing or evaluation of federally funded projects or for information that must be disclosed in order to meet the requirements of the Federal Food and Drug Administration (FDA).

The Certificate of Confidentiality does not prevent the participant or a member of their family (e.g. guardian) from voluntarily releasing information about themselves and their involvement in the research. If an insurer, employer or other person obtains the participant's written consent to receive research information, then the researcher may not use the Certificate to withhold that information.

The Certificate of Confidentiality does not prevent the researchers from disclosing voluntarily, without consent, information that would identify the individual as a participant of the research project in instances such as evidence of child or elder abuse or a participant's threatened harm to self or others.

Data Security

All electronic data will be de-identified, housed on the University of Minnesota AHC secured server. In-house access will be password protected. De-identified outcome data will be posted on a secure, password-protected website that is only available to research investigators. All identifying information will be kept separate from the data in a locked, secure place at the local site. Research study staff are required to complete site specific data security training through their institutions. There will be *no* data or consent forms placed in subject's medical records.

Data Management

Data for this study will be entered into a REDCap database, which uses a MySQL database via a secure web interface with data checks used during data entry to ensure data quality. REDCap includes a complete suite of features to support HIPAA compliance, including a full audit trail, user-based privileges, and integration with the institutional LDAP server. The MySQL database and the web server will both be housed on secure servers operated by the University of Minnesota Academic Health Center's Information Systems group (AHC-IS). The servers are in a physically secure location on campus and are backed up nightly, with the backups stored in accordance with the AHC-IS retention schedule of daily, weekly, and monthly backups retained for 1 month, 3 months, and 6 months, respectively. Weekly backup tapes are stored offsite. The AHC-IS servers provide a stable, secure, well-maintained, and high-capacity data storage environment, and both REDCap and MySQL are widely-used, powerful, reliable, well-supported systems. Access to the study's data in REDCap will be restricted to the members of the study team by username and password.

All the data servers are managed by the Academic Health Center – Information Systems (AHC-IS) virtual servers which utilize clustered infrastructure to provide real-time failover of virtual servers. This real-time clustering is physically limited to the UMN data center. All relevant AHC IS procedures related for PHI compliant servers (as required by the Center of Excellence for HIPAA Data).

The integrated data will be stored in PHI compliant servers managed by AHC IS with access given to those authorized users in the Clinical and Translation Science Institute Informatics team (CTSI BPIC and MCC CISS). The data will be integrated and extracted to researchers through the CTSI Informatics team and will be delivered through secure and compliant mechanisms (e.g. AHC IE data shelter, BOX, SFTP, etc.). If data de-identification is needed, then compliant AHC IE data de-identification tools will be used. The informatics team will grant the IRB approved study team members access to data. Key study personnel are trained on the use of these platforms and will comply with protocol specific instructions.

Data Integrity: Adherence to Protocol Procedures and Training

Standard Operating Procedures will include overall study procedures and visit procedures will be provided. Extensive training for research personnel will occur at a remote site initiation visit prior to the study start, where the protocol and procedures will be carefully described. Case Report Forms will be electronic to maximize parallel recording of data across studies and allow for remote access. Each visit will have a checklist of all the measures that need to be administered and the order by which these measures are administered. All subjective forms will be provided on web-based REDCap including the telephone screening. Additionally, conference calls will be held regularly with lead site, PIs and coordinators to review project status, accruals, and procedures. The project manager from UMN will monitor the study remotely and possibly monitor in-person at OSU once COVID travel restrictions are lifted to review study procedures, audit the documents and observe study visits. Data on REDCap will be monitored by UMN for missing data or any unusual value through data quality checks.

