10.1 Trial Endpoints

Primary Endpoint:

- The change in total NNAL from visit 00 to week 6 visit.
- The mean CPD based on 7-day IVR data between week 00 and Week 6 visit

Secondary Endpoint:

- Change in TNE, CEMA, and PheT from visit 00 to week 6 visit
- Change in intensity of smoking measured by filter analysis collected at 00, Week 3 and Week 6.
- Change in parameters of inhalation depth measured at 00 and Week 6.
- Change in subjective measures (dependence as measured by the FTND, mCES, and Perceived Health Risk) from visit 00 to Week 6 visit.

Exploratory Endpoints:

- Change in biomarkers of other volatile organic compounds (e.g.,3-HPMA, HMPMA) from visit 00 to Week 6 visit.
- Determine concordance in biomarkers of exposure across different sample collection methods.

Secondary Endpoint

Safety Endpoints:

- Adverse Events (AEs)

- Serious adverse events (SAEs)

Randomization

Subjects will be randomly assigned using a stratified (by site), block randomization scheme into the following groups: (1) ventilated filter cigarettes; or (2) unventilated filter cigarettes.

Sample size and power considerations

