To determine the sample size for a test of non-inferiority for unventilated filter cigarettes compared to ventilated filter cigarettes (control group), we used pilot data from our original ventilated/unventilated study 1 ([name], personal communication). For the purposes of sample size considerations, we will focus on total NNAL as one of the primary outcomes. Seventy subjects had a baseline NNAL value while smoking their usual brand and 19 and 16 subjects had an end of study NNAL value for the ventilated and unventilated groups, respectively. The endpoint of interest is the change in NNAL from baseline. To normalize the distribution of NNAL, the calculations were performed in the log scale. The non-inferiority margin (NIM) was set at a 15% change between groups. This criterion was chosen because it is close to, but not greater than the upper limit of the 95% confidence interval (CI) for the geometric mean of the change in NNAL. Therefore, 73 subjects per group will achieve 80% power to detect non-inferiority for the mean change in NNAL using a one-sided, two sample t-test with a significance level of 0.05. Furthermore, with these sample sizes, a one-sided, two-sample t-test for the mean difference in cigarettes per day (CPD) from baseline will have 90% power to determine non-inferiority with a significance level of 0.05 if the NIM is 2 cigarettes. A mean difference between ventilation groups of less than 2 cigarettes is considered to be in the range of equivalence. To accommodate a 10% loss-to-follow-up rate, we plan to enroll 81 subjects per group for a total of 162.

Study Populations

Intent-to-treat

The first analysis of all primary and secondary endpoints will adhere to the intent-to-treat principle. Under this principle, all subjects randomized to one of the two study arms will be included in the analysis in the group to which they were randomized regardless of protocol violations and compliance to treatment assignment.

Per-Protocol

A second per-protocol analysis will include only participants who complete the 6 week visit without protocol violations or non-compliance.

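### The primary endpoints are defined as baseline-adjusted but tested by a change-score t-test; the model with baseline and site is only supplementary and has no stated non-inferiority rule

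*Combined protocol and SAP*

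**What the plan says.** Section 10.2, Primary Endpoint Analysis, defines the first endpoint as "the total NNAL at the 6-week visit adjusted for NNAL at end of Phase 2 (visit 00") and the second as mean cigarettes per day (CPD) over the 7 days before Week 6, "adjusted for the mean CPD during Phase 2 (visit 00").

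The next paragraph, Primary Analysis, reads: "The primary analysis will be a one-sided, two-sample t-test for non-inferiority". Its hypotheses concern the increase from the end of Phase 2, with margins of 15% for NNAL (log scale) and 2.0 cigarettes for CPD. The sample size in section 10.1 rests on the same test, "using a one-sided, two sample t-test with a significance level of 0.05".

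Section 10.1 lists NNAL as a change from visit 00 to Week 6. Its CPD line is "The mean CPD based on 7-day IVR data between week 00 and Week 6 visit", which does not say whether a change is meant. On allocation it says: "Subjects will be randomly assigned using a stratified (by site), block randomization scheme".

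Under Secondary Analysis in section 10.2, the t-test "will be supplemented with multiple linear regression analysis to include the baseline (visit 00) value for NNAL or CPD and the stratification variable (site"). Subject characteristics that look unbalanced at p<0.2 are added as further covariates. On non-inferiority for these models, the plan says only: "Both linear regression models and repeated measures analysis can be modified for the equivalence and non-inferiority testing situations".

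**The concern.** An endpoint described as a Week 6 value adjusted for baseline points to analysis of covariance. The named test is an unadjusted comparison of change scores. These are different estimators. They target the same group difference under randomisation, but in a given trial they can fall on opposite sides of the margin.

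Three things follow.

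- **Precision.** NNAL is planned at only 80% power. A change score fixes the coefficient on baseline at 1. ANCOVA estimates it, and so usually has a smaller residual variance. Site, the stratification factor, is also left out of the primary test.
- **Role of the adjusted model.** It will be reported beside the t-test, for an endpoint the plan itself calls adjusted. Part of its covariate list is settled only after looking at the data, and no margin, confidence level or decision rule is attached to its estimate.
- **CPD baseline.** Section 10.2 gives it both as the mean during Phase 2, which lasts two weeks, and as the end of Phase 2 (visit 00). The days of daily text data that form it are not stated.

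**Working it through.** **Inputs from the documents** (section 10.1, Sample size and power considerations): 73 evaluable per group; one-sided alpha 0.05; NNAL margin 15% at 80% power; CPD margin 2 cigarettes at 90% power. Not given: the SD of change, the between-subject SD, and the correlation rho between visit 00 and Week 6. These are assumed or back-solved below, with true difference zero.

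**Step 1. SD implied by the plan's own power.** The plan's 73 per group cannot be reproduced forwards without an SD, so it is solved backwards. The NNAL margin is taken as ln(1.15) = 0.1398, and sqrt(2/73) = 0.1655.

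- NNAL, normal approximation: 0.1398 / ((1.645 + 0.842) × 0.1655) = 0.340. Noncentral t with 144 df: 0.338.
- CPD, normal approximation: 2 / ((1.645 + 1.282) × 0.1655) = 4.13. Noncentral t: 4.11.

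Reading the margin as -ln(0.85) would give an NNAL SD of 0.393 instead. The power comparison below would not change, because only the ratio of margin to SD enters.

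**Step 2. ANCOVA against change score, equal variances at both visits.** Var(change) = 2s²(1 - rho). ANCOVA residual variance = s²(1 - rho²). The ratio is (1 + rho)/2. Power uses noncentral t with 142 df (one fewer each for baseline and site).

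| rho | Variance ratio | NNAL power (t-test 80%) | CPD power (t-test 90%) | Implied between-subject SD, CPD | Implied between-subject SD, log NNAL |
|---|---|---|---|---|---|
| 0.5 | 0.75 | 89.0% | 95.9% | 4.11 | 0.338 |
| 0.7 | 0.85 | 85.4% | 93.7% | 5.31 | 0.436 |
| 0.8 | 0.90 | 83.5% | 92.5% | 6.50 | 0.534 |
| 0.9 | 0.95 | 81.8% | 91.3% | 9.19 | 0.756 |

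The implied SDs are SD of change / sqrt(2(1 - rho)).

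**Step 3. Which rho is plausible for CPD?** Eligibility (section 4.2) allows 5 to 35 cigarettes per day. As an illustration only, a triangular spread over that range has SD 6.12 and a uniform spread 8.66. Then rho = 1 - 4.11²/(2 × SD²) gives 0.775 and 0.887. The upper rows of rho are therefore more plausible for CPD than rho 0.5.

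**Step 4. Unequal variances.** Let k be the Week 6 SD divided by the visit 00 SD. The variance ratio becomes k²(1 - rho²)/(1 + k² - 2·rho·k).

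- k = 1.25, rho 0.8: the ratio is 1 and NNAL power is 79.995%. The regression slope k × rho equals 1 here, so the change score is already optimal and only two degrees of freedom are lost.
- k = 1.1, rho 0.9: power is 80.01%.
- k = 0.9: power is 86.8% to 91.9% for rho 0.9 to 0.5.

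**Step 5. Omitting site.** Simulation, 100,000 runs per cell, 73 per arm and 73 per site, rho 0.5, 0.8 and 0.9.

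| Site difference (log units) | t-test type I error | t-test power |
|---|---|---|
| None | 0.050 | 79.8% to 80.0% |
| Level only, 0.2 | 0.049 to 0.052 | 79.8% to 80.3% |
| Change, 0.1 | 0.048 | 79.4% to 79.6% |
| Change, 0.2 | 0.042 to 0.044 | 77.7% to 78.1% |

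A difference in level cancels from the change score. A difference in change makes the t-test mildly conservative. ANCOVA with site held type I error at 0.049 to 0.051 in every cell, with power 81.5% to 88.8% (rho 0.9 to 0.5).

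**Step 6. How often do the two analyses disagree?** Simulation, 10,000 runs, 73 per group, no true difference, baseline-only ANCOVA: opposite non-inferiority conclusions in about 13%, 9% and 8% of trials at rho 0.5, 0.7 and 0.8.

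**The case against.** The plan names one primary test, with hypotheses, both margins, the log scale for NNAL and a significance level, and it sizes the trial on that test. A reader can tell that the t-test decides. The word adjusted may be loose usage for change: section 10.1 words NNAL as a change, the sample size paragraph treats CPD relative to baseline, and the hypotheses in section 10.2 speak of an increase for both. The adjusted regression is already pre-specified, and a supportive analysis does not strictly need its own decision rule. The t-test is valid, and the power gain rests on quantities the documents do not give.

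Most of this stands. The missing rule concerns the regression and mixed model, not the primary t-test. The gain is only a few points at high correlation, and a 10% larger SD at Week 6 can remove most or all of it. Three things remain. The endpoint definition and the test do not describe the same analysis. The CPD baseline is worded in more than one way. And the supplementary model has data-dependent covariates and no margin attached, although it can contradict the t-test in a noticeable share of trials. Section 10.2 also makes baseline-adjusted regression the main model for the FTND, a secondary endpoint, so the adjustment is used there but withheld from the primary test.

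**Conclusion.** The point holds as a matter of efficiency and clarity. It does not make the planned analysis invalid: there is no bias and no inflated type I error. Under equal variances and rho 0.8 to 0.9, moving to ANCOVA is worth about 2 to 4 points of NNAL power and 1 to 3 points of CPD power at 73 per group. At rho 0.5 to 0.7 it is worth about 5 to 9 and 4 to 6 points. It can be worth essentially nothing if Week 6 values are more variable than baseline values, but the loss is then negligible. These figures rest on an SD of change back-solved from the stated power, a true difference of zero, and an assumed correlation and variance ratio. The inconsistency in wording rests on no assumption. The change should be made, though the trial would remain interpretable without it.

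**What to change.** - Make ANCOVA the primary analysis: Week 6 log NNAL, or Week 6 mean CPD, on group, the corresponding baseline value and site, with no covariates chosen by observed imbalance.
- Declare non-inferiority if the upper one-sided 95% confidence limit for the group effect (unventilated minus ventilated) is below ln(1.15) for NNAL, or below 2.0 cigarettes for CPD.
- Keep the change-score t-test as a named sensitivity analysis, and state that the ANCOVA estimate decides.
- Word the endpoints in sections 10.1 and 10.2 to match this model, and state exactly which days of daily text data form the baseline CPD.
- Add a sentence to the sample size paragraph that 73 per group was derived for the t-test and is retained.

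The cost is wording in the statistical sections only: no new data, assays, visits or subjects.
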